9.1.1. Assessment of Severity

The Investigator will assess the intensity of the AE and rate the AE as mild, moderate, or severe using the following criteria:

Grade 1 – Mild: These events are easily tolerated, require minimal or no treatment, and do not interfere with the subject’s daily activities.

Grade 2 – Moderate: These events cause sufficient discomfort to interfere with daily activity and/or require a simple dose of medication, e.g., analgesics or anti-emetics.

Grade 3 – Severe: These events incapacitate and prevent usual activity or require complex medication/treatment or hospitalization.

Grade 4 – Life Threatening: These events are those for which the subject was at risk of death at the time of the event rather than an event which hypothetically might have caused death if it were more severe.

Grade 5 – Death: The event resulted in the death of the subject.

Changes in the severity of an AE should be documented to allow for an assessment of the duration of the event at each level of intensity to be performed.

9.1.2. Assessment of Causality

The Investigator will assess the relationship or association of the investigational product and the study procedure (intratympanic injection) in causing or contributing to the AE, which will be characterized using the following classification and criteria:

- **Related** – The AE is known to occur with the study intervention, there is a reasonable possibility that the study intervention caused the AE, or there is a temporal relationship between the study intervention and event. Reasonable possibility means that there is evidence to suggest a causal relationship between the study intervention and the AE.

- **Not Related** – There is not a reasonable possibility that the administration of the study intervention caused the event, there is no temporal relationship between the study intervention and event onset, or an alternate etiology has been established.

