9. ADVERSE EVENT REPORTING

Timely, accurate, and complete reporting and analysis of safety information from clinical trials will be conducted in accordance with Good Clinical Practice.

Adverse events will be monitored and documented starting during and after administration of investigational product until study participation is complete.

All AEs and serious adverse events (SAEs) that are reported or observed during or after dosing with the investigational product will be recorded on the AE page of the eCRF for all enrolled subjects.

Information to be collected includes description of event, affected ear (for ear-related events only), date of onset, Investigator-specified assessment of the severity and relationship to investigational product, relationship to the intratympanic injection, date of resolution of the

event, seriousness, any required treatment or evaluations, and outcome. Adverse events resulting from concurrent illnesses, reactions to concurrent illnesses, reactions to concurrent medications, or progression of disease states must also be reported. Perforations of the tympanic membrane will be captured as AEs if the perforation does not resolve by the end of the study or increases in size.

If the existing medical condition worsens at any time after the injection (e.g., requires intervention or treatment), it should be recorded as an AE (e.g., worsening tinnitus [identify L, R, or both ears]).

Wherever possible, a specific disease or syndrome rather than individual associated signs and symptoms should be identified by the Investigator and recorded on the eCRF using medical terminology. However, if an observed or reported sign or symptom is not considered a component of a specific disease or syndrome by the Investigator, it should be recorded as a separate adverse event on the eCRF. Additionally, the condition that led to a medical or surgical procedure (e.g., surgery, endoscopy, tooth extraction, or transfusion) should be recorded as an adverse event, not the procedure.

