9.2. Monitoring of Adverse Events

9.2.1. All Adverse Events

All AEs will be analyzed for safety. Those meeting the definition of SAE must be reported using the SAE Form within the electronic data capture system eCRF. Subjects should voluntarily report any AEs or report AEs in response to general, non-directed questioning (e.g., "How has your health been since the last visit?"). For each AE volunteered by the subject, the Investigator should obtain all the information required to complete the AE page of the eCRF, in accordance with the guidelines that accompany it.

All AEs, regardless of seriousness, severity, or presumed relationship to investigational product or to study procedure, must be recorded using medical terminology in the source document and on the eCRF. Whenever possible, diagnoses should be given when signs and symptoms are due to a common etiology (e.g., cough, runny nose, sneezing, sore throat, and head congestion should be reported as "upper respiratory infection"). Investigators must record on the eCRF their opinion concerning the relationship of the AE to investigational therapy and to study procedure. All measures required for AE management must be recorded in the source document and reported according to Sponsor instructions.

Any non-serious AE that occurs after administration of investigational product must be reported in detail on the appropriate eCRF page and followed until resolution, stabilization, or the End of Study Visit. The description of the AE will include description of event, date of onset, date of resolution, Investigator assessment of severity and relationship to investigational product and to study procedure (with rationale), seriousness (with rationale), any required treatment or evaluations, and outcome (e.g., fatal, not resolved, resolved, resolved with sequelae, unknown).

The Sponsor assumes responsibility for appropriate reporting of AEs to the regulatory authorities. The Sponsor will also report to the Investigators all SAEs that are unlisted in the Investigator's Brochure and associated with the use of the investigational product. The Investigators must report these events to the appropriate Institutional Review Board (IRB) or Ethics Committee (EC) in accordance with local regulations.

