11.4.3.1. Adverse Events

The primary analysis of AEs will consider only treatment-emergent adverse events (TEAEs), events occurring for the first time, or worsening during or after the first dose of investigational product. Subject incidence of TEAEs and SAEs will be tabulated by Preferred Terms (PTs) and System Organ Class (SOC). Severity and relationship to investigational product will also be presented. For summary tables, a subject who experiences the same coded event more than once is counted only one time for that coded event at the highest severity level. AEs will be presented by descending order of frequency in MedDRA SOC and PT.

Listings of all SAEs, AEs leading to study withdrawal, and deaths on-study will also be included. Duration and outcome of each AE will be reported in subject listings.

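### Section 9.1.2 defines Related and Not Related by overlapping lists with no tie-break, so the same adverse event can be coded either way within the protocol

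*Combined protocol and SAP*

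**What the plan says.** Section 9.1.2 of the protocol asks the investigator to judge the part played by the product and by the injection procedure in each adverse event. It offers two categories, each a list joined by an or:

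- Related: "The AE is known to occur with the study intervention", or "there is a reasonable possibility that the study intervention caused the AE, or there is a temporal relationship between the study intervention and event".
- Not Related: "There is not a reasonable possibility that the administration of the study intervention caused the event", or "there is no temporal relationship between the study intervention and event onset, or an alternate etiology has been established".

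One term is defined: "Reasonable possibility means that there is evidence to suggest a causal relationship between the study intervention and the AE". Temporal relationship has no definition and no time window, and the section gives no rule for an event that meets a criterion from each list. Section 9.1 defines an adverse event as something that arises or worsens after the product is given.

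The answer is used in three places. Section 11.4.3.1 says of treatment-emergent events: "Severity and relationship to investigational product will also be presented". Section 9.2.1 has the sponsor inform investigators of serious events that are unlisted in the Investigator's Brochure and "associated with the use of the investigational product"; investigators then report these to the IRB or EC. Section 14.6.1 has the Safety Review Committee consider findings suspected to be related to product or procedure, alongside any adverse events. Section 9 collects relationship to product and "relationship to the intratympanic injection" as distinct items, and Section 9.2.1 asks for a rationale.

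**The concern.** Two categories that are meant to split all events should be complements. The complement of a list joined by or is the set of negated criteria joined by and. Here both lists use or, and the second adds a criterion (alternate etiology) that is not the negation of anything in the first.

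Take a cold two days after the injection. Timing makes it Related; the established other cause makes it Not Related. In the other direction, an event with evidence of a causal link but no clear temporal relationship is Related on the first ground and Not Related on the second. In each case either coding follows the text, so a monitor cannot call either one wrong. The rationale records which route was taken but does not settle which was right.

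The missing definition of temporal relationship makes this worse. Every adverse event follows dosing by definition, so on a literal reading every event could be Related. With about 55 sites, the summary by relationship to product would then partly reflect how each investigator reads the section.

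**Working it through.** The plan states no figure on this point, so there is nothing to reproduce. The check is a count of logical cases.

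**Inputs, all from Section 9.1.2.** Four yes/no facts: K, known to occur with the intervention; R, reasonable possibility; T, temporal relationship; A, alternate etiology established.

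**Rules as written.**

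- Related = K or R or T
- Not Related = (not R) or (not T) or A

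**Literal count.** There are 2 × 2 × 2 × 2 = 16 combinations.

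- Related only requires R and T true and A false, with K free: 2.
- Not Related only requires K, R and T all false, with A free: 2.
- Neither would require R both true and false: 0.
- Both: 16 − 2 − 2 = 12.

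**Sensitivity to how the terms are read.**

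| Reading | Combinations | Both | Related only | Not Related only |
|---|---|---|---|---|
| Literal | 16 | 12 | 2 | 2 |
| K left out | 8 | 5 | 1 | 2 |
| T means simply after dosing, so always true | 8 | 6 | 2 | 0 |
| R implies T | 12 | 8 | 2 | 2 |
| R implies T and rules out A | 10 | 6 | 2 | 2 |
| As the row above, K left out | 5 | 2 | 1 | 2 |

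No row has a combination that meets neither definition. In the third row no event can be Not Related only. In the last row the two overlapping cases are those with a temporal relationship but no reasonable possibility, with and without an alternate etiology. The overlap shrinks under stricter readings but does not vanish under any of them.

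**Check of possible repairs, over the 16 combinations.**

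- Related if R, Not Related otherwise: 8 and 8, none in both, none in neither.
- Present lists, with Related prevailing: 14 Related, 2 Not Related, none in both.
- Present lists, with Not Related prevailing: 2 Related, 14 Not Related, none in both.
- Not Related = (not R) and (not T), with alternate etiology dropped as a separate route: still 2 in both (K true, R and T false).

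**The case against.** The strongest reply is that this is a drafting ambiguity with little reach. Much of that stands.

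- **A reader might infer that most adverse events fit both categories.** The documents do not support this. The 16 cases are logical combinations and nothing gives their frequency. Some are barely coherent, since evidence of a causal link sits poorly with an established other cause. On the narrowest reading above, the overlap is 2 of 5.
- **A reader might infer that relatedness drives safety reporting.** Mostly it does not. All adverse events are recorded whatever their presumed relationship (Section 9.2.1). All serious events go to the safety desk within 24 hours (Section 9.2.2), are followed up (Section 9.1.3) and are reviewed by sponsor and CRO (Section 14.6), all regardless of relatedness. For unlisted serious events, Section 9.2.1 does not say that the sponsor's judgement of association is simply the site's coding.
- **A reader might infer that a real signal could be lost.** Section 11.4.3.1 tabulates all treatment-emergent and serious events by arm without regard to relatedness, and lists serious events, deaths and events leading to withdrawal. A miscoded relationship removes nothing from these. The Safety Review Committee also sees the accumulated adverse event, laboratory, ear, hearing and C-SSRS data however events are coded.
- **A reader might infer that the product and procedure ratings cannot be told apart.** They are separate items with a rationale. Only the temporal criterion cannot separate them, because product and injection are given at the same moment.
- **A reader might infer that a summary by relationship to the injection is missing.** Section 11.4.3.1 names only the product, but Section 11.4.1 says that all collected data will be summarized descriptively, and Section 11.1 leaves detail to the SAP.

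Section 9.2.1 also mentions guidelines accompanying the adverse event page, which are not in the documents and might help sites. What the reply does not answer is that the rule in Section 9.1.2 itself sorts one event both ways and gives no tie-break.

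**Conclusion.** The point holds as a defect in a stated rule. Related and Not Related are not mutually exclusive, no precedence is given, and the undefined temporal criterion could make every adverse event Related. The 12 of 16 count measures the logical overlap only. It rests on reading each or as making every listed criterion sufficient alone, which is how the section is written.

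The practical effect is confined to three uses: the summaries by relationship to product, possibly which unlisted serious events are treated as associated with the product, and one of several inputs to the Safety Review Committee. The primary endpoint and other efficacy results are untouched, as are event capture, expedited site reporting, review of serious events and the overall treatment-emergent tables. Investigators rate causality blind to treatment, so the ambiguity adds inconsistency to the relationship summaries and gives no evident reason for it to favor one arm.

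**What to change.** Either of two changes to Section 9.1.2 would do.

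1. **Make the categories complements.** Rest both on reasonable possibility as the section already defines it: Related if there is evidence to suggest a causal relationship, Not Related otherwise. Ask the question separately for the product and for the injection. List known effects, timing and alternate etiology as evidence to weigh, with none of them decisive alone.
2. **Keep the lists and add a precedence rule** that makes the categories mutually exclusive. This also needs a definition of temporal relationship. If Related prevails and timing means only after dosing, every event becomes Related and the field carries no information.

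Changing one or to and within Not Related is not enough, as the last repair in the check shows.

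The cost is one reworded paragraph, re-training text for sites, and queries on events already coded. The first option also narrows Related somewhat, because known occurrence or timing alone would no longer suffice; the sponsor should accept that knowingly or choose the second.

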9.1.3. Follow up of Adverse Events

The Investigator will follow a non-serious AE until resolution, stabilization, or the End of Study Visit. The Investigator will follow an SAE (regardless of relationship to investigational product or study procedure) until the event resolves, stabilizes, or becomes non-serious. All AEs identified on the last scheduled contact must be recorded on the AE page of the eCRF and current status (ongoing or resolved) will be noted. In addition, SAEs will be reported to Medpace Clinical Safety (email: [contact]) according to the reporting guidelines identified in [Section 9.2.2](#).

9.2. Monitoring of Adverse Events

9.2.1. All Adverse Events

All AEs will be analyzed for safety. Those meeting the definition of SAE must be reported using the SAE Form within the electronic data capture system eCRF. Subjects should voluntarily report any AEs or report AEs in response to general, non-directed questioning (e.g., "How has your health been since the last visit?"). For each AE volunteered by the subject, the Investigator should obtain all the information required to complete the AE page of the eCRF, in accordance with the guidelines that accompany it.

All AEs, regardless of seriousness, severity, or presumed relationship to investigational product or to study procedure, must be recorded using medical terminology in the source document and on the eCRF. Whenever possible, diagnoses should be given when signs and symptoms are due to a common etiology (e.g., cough, runny nose, sneezing, sore throat, and head congestion should be reported as "upper respiratory infection"). Investigators must record on the eCRF their opinion concerning the relationship of the AE to investigational therapy and to study procedure. All measures required for AE management must be recorded in the source document and reported according to Sponsor instructions.

Any non-serious AE that occurs after administration of investigational product must be reported in detail on the appropriate eCRF page and followed until resolution, stabilization, or the End of Study Visit. The description of the AE will include description of event, date of onset, date of resolution, Investigator assessment of severity and relationship to investigational product and to study procedure (with rationale), seriousness (with rationale), any required treatment or evaluations, and outcome (e.g., fatal, not resolved, resolved, resolved with sequelae, unknown).

The Sponsor assumes responsibility for appropriate reporting of AEs to the regulatory authorities. The Sponsor will also report to the Investigators all SAEs that are unlisted in the Investigator's Brochure and associated with the use of the investigational product. The Investigators must report these events to the appropriate Institutional Review Board (IRB) or Ethics Committee (EC) in accordance with local regulations.

9.2.2. Serious Adverse Events

All SAEs occurring after administration of investigational product must be reported to Medpace Clinical Safety within 24 hours.

The initial report of an SAE should be made via the electronic data capture system SAE eCRF. The system will alert the Safety team and appropriate action will commence. If a SAE occurs and access to EDC is not practical within the 24-hour time frame, [REDACTED] can be notified via email or telephone.

[REDACTED]

[REDACTED]

[REDACTED]

[REDACTED]

[REDACTED]

[REDACTED]

[REDACTED]

The Investigator must provide the minimal information: i.e., protocol number, subject's initials and date of birth, subject number or medication code number, nature of the AE and Investigator's attribution.

The cause of death of a subject in a clinical study, whether the event is expected or associated with the investigational product, is an SAE.

All oral reports of an SAE must be confirmed within 24 hours by a written, more detailed report and signed by the Investigator. Source documents will be requested from the study sites for the SAE. If the subject is hospitalized during the study, a copy of the hospital discharge summary should be provided as soon as it becomes available.

The Investigator must continue to follow the subject until the SAE has subsided or until the condition becomes chronic in nature, stabilizes (in the case of persistent impairment) or the subject dies. Within 24 hours of receipt of follow-up information, the Investigator must update the SAE form electronically in the EDC system for the study and submit any supporting documentation (e.g., subject discharge summary) to Medpace Clinical Safety via Fax or email. If it is not possible to access the EDC system, refer to the procedures outlined above for initial reporting of SAEs.

All SAEs that have not resolved by the end of the study, or that have not resolved upon discontinuation of the subject's participation in the study, must be followed until either:

- the event resolves,
- the event stabilizes, or
- the event becomes non-serious.

9.2.3. Pregnancies

Pregnancies occurring after administration of the investigational product and during participation of the study are considered immediately reportable events. While not considered an SAE unless a serious criterion is met, pregnancies occurring in subjects enrolled on the study must be reported and followed to outcome. The Investigator should complete the Exposure In Utero form within one (1) working day of knowledge of the pregnancy. The pregnancy will be followed until information of the final outcome becomes available and a follow-up Exposure in Utero form is completed. Spontaneous abortions should always be reported as SAEs.

10. SUBJECT COMPLETION

10.1. Completion

Study subject participation is complete after Week 16 (Visit 6). Subjects who discontinue the study before completion of Week 16 (Visit 6) will not be considered to have completed the study.

10.2. Study Discontinuation

All subjects have the right to withdraw from study evaluations at any time, for any reason, without prejudice; nonetheless, Investigators should attempt to encourage subjects to complete the protocol so that continued observation and follow-up measurements may be obtained.

Subjects may be discontinued from the study for any of the following:

- Withdrawal of consent
- Lost to Follow-up
- Adverse Event
- Principal Investigator decision
- Sponsor decision
- Protocol deviation
- Other

At any point, the Investigator may discontinue the subject's study participation at the discretion of the Investigator or at the request of the subject, and ensure the subject receives appropriate medical care; the Investigator may also consult the medical monitor to discuss out-of-range test results.

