5.3. Blinding

The study will be double-blinded. Each treatment syringe will be prepared according to the detailed instructions in the Pharmacy Manual.

In case of emergency, the blind should be broken for site personnel only if knowing the subject's treatment allocation would facilitate specific medical treatment. In all cases, the Investigator should consult with the medical monitor prior to unblinding, and if not possible as soon as it is practical after unblinding has occurred and treatment initiated.

If the blind is broken, the subject will continue to be followed and evaluated per-protocol. The date, time, and reason for the unblinding must be documented on the appropriate page of the eCRF.

The randomization schedule or blocking factor(s) will not be revealed to study subjects, Investigators, clinical staff, site managers or the Sponsor until all subjects have completed the study and the database has been finalized by the Sponsor.

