7.1. Prohibited Therapy During the Study Period

The following therapies are prohibited during the study:

- Phenol for use in anesthetizing the tympanic membrane
- Intratympanic injection other than that outlined in the current study
- Systemic corticosteroids (inhaled and nasal steroids are permitted)
- Other investigational drug(s) or device(s)
- Other NMDA receptor antagonists (e.g., memantine, dextromethorphan). Note, occasional use of dextromethorphan for cough suppression is allowed except during

the period 7 days prior to Baseline and 7 days after the injection of the investigational product.

- Medications known as potentially tinnitus-inducing (e.g., aminoglycosides, ototoxic chemotherapeutic drugs, high doses of intravenous loop diuretics, quinine, high doses of aspirin or other non-steroidal anti-inflammatory drugs). Usage of low doses of aspirin (e.g., daily doses of 81 mg) or low doses of other non-steroidal anti-inflammatory drugs for intermittent pain relief may be permitted at the Investigator's discretion.
- Medications that are considered moderate or strong inducers of CYP2B6 (e.g., carbamazepine, efavirenz, rifampin, and ritonavir)

Use of any of these prohibited therapies will be considered a protocol deviation.

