10.2.2. Replacements

Subjects who discontinue participation in the study for any reason after dosing will not be replaced. The sample size was estimated to account for an assumed discontinuation rate of 15% by Week 8.

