11.2. Analysis Sets

The all enrolled set will include all subjects who sign an informed consent form.

The full analysis set (FAS) includes all randomized subjects, and they will be included in the group to which they were randomized.

The per-protocol analysis set (PP) includes all subjects in the full analysis set that provide TFI data at Weeks 4 and 8, and do not have any protocol deviations that may impact the outcome of the TFI overall score.

The safety analysis set includes all subjects who receive study treatment, and they will be included in the treatment group based on the treatment received.

The FAS and PP sets will be used for efficacy analyses. The safety analysis set will be used for all safety analyses.

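### Section 10.2 permits ending follow-up for a protocol deviation after a one-time injection, which can cause avoidable and possibly informative loss of the Week 4 or Week 8 TFI

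*Combined protocol and SAP*

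**What the plan says.** Section 10.2 states "Subjects may be discontinued from the study for any of the following" and then gives a list that includes "Protocol deviation", next to principal investigator decision, sponsor decision and a residual category. It adds: "At any point, the Investigator may discontinue the subject's study participation at the discretion of the Investigator". The same section, in its sentence on the right to withdraw, says that "Investigators should attempt to encourage subjects to complete the protocol so that continued observation and follow-up measurements may be obtained".

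Other sections bear on what removal does:

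- **Treatment (6.2):** one intratympanic injection by a physician on Day 1, with no later dosing.
- **Deviations (7.1):** after a list that includes systemic corticosteroids, other intratympanic injections and other NMDA antagonists, "Use of any of these prohibited therapies will be considered a protocol deviation".
- **Analysis sets (11.2, 11.4.2):** "The full analysis set (FAS) includes all randomized subjects", and all efficacy endpoints use this set. The per-protocol set requires TFI data at Weeks 4 and 8 and no deviation liable to affect the TFI.
- **Primary endpoint (11.4.2.1):** a TFI fall of 13 points or more at Week 4 and again at Week 8. Missing data are multiply imputed, by a method left to the SAP.
- **Unblinding (5.3):** "If the blind is broken, the subject will continue to be followed and evaluated per-protocol".
- **Replacement (10.2.2):** subjects lost after dosing are not replaced, and the sample size allows for an "assumed discontinuation rate of 15% by Week 8".

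**The concern.** In a trial with repeated dosing, discontinuation after a deviation may at least stop exposure. Here, once the injection has been given, nothing remains to stop, so the only effect of removal is that later assessments are not made. That works against an analysis of everyone randomized, and against the aim of continued follow-up stated in 10.2 itself.

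The loss may also be related to outcome. A subject whose tinnitus persists could plausibly seek a systemic steroid or another intratympanic treatment. Both are deviations under 7.1, and either could lead to removal before Week 8. If imputation then treats that subject like those who stayed, response in that arm is overstated.

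Removal gains nothing at analysis. The per-protocol set already excludes deviations that matter for the TFI. Because that set also requires the Week 4 and Week 8 scores, removing someone early for a harmless deviation loses the subject from the per-protocol analysis too.

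**Working it through.** **1. The plan's own figure.** Inputs from section 11.5: 43% versus 18%, two-sided 0.05, 60 evaluable per arm. The pooled two-proportion z power is

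Φ( [Δ − 1.96·√(2·p̄·(1−p̄)/n)] / √([p₁(1−p₁)+p₂(1−p₂)]/n) )

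with Δ = 0.25, p̄ = 0.305 and n = 60:

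- null standard error √(2 × 0.305 × 0.695 / 60) = 0.0841, times 1.96 = 0.1648
- alternative standard error √((0.2451 + 0.1476) / 60) = 0.0809
- (0.25 − 0.1648) / 0.0809 = 1.05, power 85.4%

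This reproduces the stated figure of about 85%. For attrition, 120 / 0.85 = 141.2, or 142 with equal arms. The planned 140 leaves 140 × 0.85 = 119 evaluable (59.5 per arm), with power 85.1%. The sample size is sound.

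**2. Power against total loss by Week 8, 70 randomized per arm.**

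| Loss | Evaluable per arm | Power |
|---|---|---|
| 15% | 59.5 | 85.1% |
| 10% | 63 | 87.1% |
| 5% | 66.5 | 88.8% |
| 2% | 68.6 | 89.8% |
| 0% | 70 | 90.3% |

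These rows describe loss from every cause. The share due to deviations is not given, so the gain from this change alone lies somewhere within the range and cannot be fixed further.

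**3. Bias, as an illustration only.** Assume true rates of 43% and 18%, that every removed subject is a true non-responder, and that imputation gives each the observed rate of the arm. With removal fractions d_A (active) and d_P (placebo), the estimated difference is 0.43/(1−d_A) − 0.18/(1−d_P), against a true 25.0 points.

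| d_A | d_P | Estimated difference |
|---|---|---|
| 5% | 5% | 0.4526 − 0.1895 = 26.3 points |
| 10% | 5% | 0.4778 − 0.1895 = 28.8 points |
| 0% | 10% | 0.4300 − 0.2000 = 23.0 points |

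The removal fractions are assumptions. The last row shows that the treatment difference can be understated as well as overstated.

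**4. How the endpoint limits this.** Response needs success at both visits, so an observed Week 4 failure settles non-response whatever happens at Week 8. If half of the removed non-responders in the 5%-per-arm case had already failed at Week 4, only 2.5% per arm would be wrongly imputed: 0.25 / 0.975 = 25.6 points instead of 26.3.

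**5. The follow-up rules side by side.** Section 5.3 keeps an unblinded subject in follow-up, and Table 1, footnote 8, has a subject found pregnant after dosing complete the 16 weeks. No section says the same for a subject with a deviation.

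**The case against.** The strongest reply is that 10.2 says subjects may be discontinued, mixes disposition outcomes such as loss to follow-up with reasons to act, and itself urges continued follow-up. Nothing directs a site to remove a subject who takes a steroid; 7.1 only classes it as a deviation. That is right. A reader might infer that deviators must be dropped, or that 10.2 contradicts 5.3. The text supports neither, since 5.3 covers a different event. What stands is that removal is open to any site and no section closes it.

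Second, post-baseline data are not all lost. Table 1 schedules the TFI at Visit 6 or early termination, and its footnote 2 calls for end-of-study procedures on early termination generally. This helps, but one such visit cannot supply both scheduled scores, and the available text gives no rule assigning it to Week 4 or Week 8.

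Third, the imputation method is deferred to the SAP and its description is not in the text available. A model using earlier TFI scores would reduce the bias illustrated above. The illustration is therefore not a prediction.

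Fourth, the outcome-related trigger is narrow. Some 7.1 items, such as phenol anesthesia or CYP2B6 inducers, have no stated link to response, and 7.2 says changes in concomitant medication, devices or behavioral therapy are not deviations. Steroids and other intratympanic injections remain.

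**Conclusion.** The point holds as a preventable weakness in the follow-up rules. Section 10.2 permits loss of primary-endpoint data for a reason that serves neither treatment nor analysis, and the loss may be related to outcome. Only removal before the Week 8 visit affects the primary endpoint.

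The size is unknown. A reader might infer that the trial is underpowered or that the treatment effect will be overstated. The documents do not support either. Planned power of about 85% already absorbs 15% loss, and the rise to 90.3% would require no attrition of any kind. The illustrated differences of 23.0 to 28.8 points, against a true 25.0, rest on assumed removal rates, on all removed subjects being non-responders and on imputation at the arm's observed rate. An observed Week 4 failure, an early-termination TFI or imputation that uses earlier scores would shrink them. The case for change is that the data can be kept at almost no cost, so there is no need to rely on imputation to recover them.

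**What to change.** Delete protocol deviation from the 10.2 list. Deleting it alone would leave the same removal possible under another label, so add text to this effect:

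*A protocol deviation alone, including use of a therapy listed in 7.1, is not a reason to end follow-up, whether recorded as a deviation, as a principal investigator or sponsor decision, or as other. These subjects continue the scheduled TFI visits and are analysed in the FAS as randomized, with their observed TFI. Deviations are handled through the PP set as a supporting analysis.*

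Withdrawal of consent, loss to follow-up, adverse events and the investigator's safety discretion stay unchanged. The text governs data collection and analysis only and alters no treatment decision.

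The cost is a few lines in the next amendment. The visits are already in Table 1 and no procedure is added. The downside is that the FAS result then includes TFI observed after prohibited therapy, so it estimates the effect of assignment whatever therapy follows. The SAP should say so openly.
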